## Statistical Analysis Plan (SAP) for Non-Interventional Studies (NIS) BI Study Number 1160-0304

Page 15 of 27

#### 6.2.3.5 Month $12 \pm 6$ weeks (Visit 5)

The following procedures will be performed at 12 months after the baseline. Data will be collected from the medical charts and recorded on the CRF when they are available.

- Record the weight and alcoholic status (defined as  $\geq 8$  units of consumption per week)
- Record the active or newly onset of comorbidities since the visit 4 (during Month 9 to Month 12). Comorbidities include hypertension, diabetes, congestive heart failure, vascular disease (myocardial infarction, peripheral artery disease, and complex aortic plaque), ischemic heart disease, left ventricular dysfunction, stroke, transient ischemic attack, thromboembolism, abnormal kidney function (chronic dialysis, renal transplantation, serum creatinine ≥ 200 μmol/L, or eGFR < 60 mL/min/1.73 m²), abnormal liver function (chronic hepatic disease [e.g., cirrhosis] or biochemical evidence of significant hepatic derangement [e.g., bilirubin > 2 × upper limit of normal, in association with AST/ALT/ALP > 3 × upper limit normal]), major bleeding, and predisposition to bleeding/anemia.
- Collect the results of serum creatinine (will be used to calculate CrCl by Cockcroft-Gault formula) and eGFR if available in medical record. Only the values within the allowed window and closest to 12 months will be collected.
- To acquire HAS-BLED score:
  - Record the results of bilirubin, AST, ALT, ALP, INR and PT if available in medical record. Only the values within the allowed window and closest to 12 months will be collected.
  - Record if the subject is receiving chronic dialysis or have undergone renal transplant due to abnormal renal function, and medication usage predisposing to bleeding (antiplatelet agents or NSAIDs) during 9 to 12 months
- Record the use of dabigatran (dose, date of administration)
- Record the change of concomitant therapies for AF or stroke prevention since the last visit (generic name or name of the therapy)
- Complete the measurement of MMAS-8 score
- Record the occurrence of stroke and thromboembolic events, if any
- Record the occurrence of bleeding-related events, if any
- Do safety reporting if any dabigatran relevant ADR, fatal AEs, and pregnancies occurs

#### 6.2.4 Study discontinuation

Boehringer Ingelheim reserves the right to discontinue the study overall or at a particular study site at any time for the following reasons:

- (1) Failure to meet expected enrolment goals overall or at a particular study site
- (2) Emergence of any efficacy/safety information that could significantly affect the continuation of the study, or any other administrative reasons.

## Statistical Analysis Plan (SAP) for Non-Interventional Studies (NIS) BI Study Number 1160-0304

Page 16 of 27

(3) Violation of Good Clinical Practice (GCP), Good Epidemiological Practice (GEP), or Good Pharmacoepidemiology Practice (GPP) (as applicable), the study protocol, or the contract by a study site or investigator, disturbing the appropriate conduct of the study

The investigator/the study site will be reimbursed for reasonable expenses incurred in case of study termination (except in case of the third reason).

#### 7. VARIABLES

#### 7.1.1 Exposures

Being an NIS, the prescription of dabigatran will be in accordance with the Summary of Product characteristics and physician's discretion. Treatment record of dabigatran will be collected and recorded on CRF across the 12 months of study period. Data to be collected include start/end date of administration, dose, and the reason for dose adjustment or interruption.

Mean daily dose of dabigatran will be summarize by study group. If dabigatran treatment recorded in CRF had discontinued (that's the end date of administration had been recorded), the dabigatran treatment duration will be the time range of start/end date of administration. However, if dabigatran treatment recorded in CRF is ongoing, the dabigatran treatment duration will be the time range of start date of administration to the date of last dabigatran treated.

#### 7.1.2 Outcomes

#### 7.1.2.1 Primary outcomes

The proportion of patients with high adherence to dabigatran treatment which is defined as achieving the MMAS-8 score of 8 points at 12 months in patients with and without advanced educational intervention

- The MMAS-8 is an 8-item structured, self-report measure that assesses medication adherence. It has been proved to be a valuable resource to address adherence concerns, such as forgetting to take medications or discontinuing medications without guidance. If a patient scores higher on the scale, they are evaluated as more adherent. If they score lower on the scale, they are presumed to be struggling with non-adherence.
- The validated Chinese MMAS-8 will be used to evaluate the adherence to dabigatran at baseline and every follow-up visit. Patients are considered to have low adherence with scores less than 6, medium adherence with scores of 6 to 7, and high adherence with a score of 8.

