9.2.2.1 Inclusion criteria

Patients can be included if ALL the following criteria are met:

- (1) Provide written informed consent prior to participation
- (2) Female or male adult patients aged \geq 20 years and < 75 years, newly diagnosed with non-valvular atrial fibrillation (NVAF) within 1 month and has newly prescribed with dabigatran on physician's decision before study enrolment.

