9.2.3.2 Month 3 ± 6 weeks (Visit 2)

The following procedures will be performed at 3 months after the baseline. Data will be collected from the medical charts and recorded on the CRF when they are available.

- Record the weight and alcoholic status (defined as ≥ 8 units of consumption per week)
- Record the active or newly onset of comorbidities since the baseline (during baseline to Month 3). Comorbidities include hypertension, diabetes, congestive heart failure, vascular disease (myocardial infarction, peripheral artery disease, and complex aortic plaque),

NIS Protocol Page 22 of 46

ischemic heart disease, left ventricular dysfunction, stroke, transient ischemic attack, thromboembolism, abnormal kidney function (chronic dialysis, renal transplantation, serum creatinine $\geq 200~\mu mol/L$, or eGFR $<60~mL/min/1.73~m^2$), abnormal liver function (chronic hepatic disease [e.g., cirrhosis] or biochemical evidence of significant hepatic derangement [e.g., bilirubin $>2~\times$ upper limit of normal, in association with AST/ALT/ALP $>3~\times$ upper limit normal]), major bleeding, and predisposition to bleeding/anemia.

- Collect the results of serum creatinine (will be used to calculate CrCl by Cockcroft-Gault formula) and eGFR if available in medical record. Only the values within the allowed window and closest to 3 months will be collected.
- To acquire HAS-BLED score:
 - Record the results of bilirubin, AST, ALT, ALP, INR, and PT if available in medical record. Only the values within the allowed window and closest to 3 months will be collected.
 - Record if the subject is receiving chronic dialysis or have undergone renal transplant due to abnormal renal function, and medication usage predisposing to bleeding (antiplatelet agents or NSAIDs) during baseline to 3 months
- The educator delivers advanced education to subjects in the experimental group.
- Record the use of dabigatran (dose, date of administration)
- Record the change of concomitant therapies for AF or stroke prevention after baseline (generic name or name of the therapy)
- Complete the measurement of MMAS-8 score
- Record the occurrence of stroke and thromboembolic events, if any
- Record the occurrence of bleeding-related events, if any
- Do safety reporting if any dabigatran relevant ADR, fatal AEs, and pregnancies occurs

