9.7.1 Main analysis

The analyses will be mainly descriptive to gain an understanding of the characteristics of the sample studied.

Continuous variables will be reported as number, mean, standard deviation (SD), minimum, maximum, and 95% confidence interval (CI). Categorical variables will be summarized as number and frequency or percentage with observed (non-missing) data.

Analysis of endpoints:

- The primary outcome is to describe the proportion of patients with high adherence to dabigatran treatment which is defined as achieving MMAS-8 score of 8 points at 12 months for each group. Subjects without MMAS-8 value recorded at 12 months will be excluded from the analysis of primary endpoint.
- The Mean MMAS scores at 3, 6, 9 and 12 months will be compared between patients with and without advanced educational intervention using Chi-square, Fisher's exact, or other appropriate tests for categorical data and using t-test or Wilcoxon rank-sum test for continuous data. Similarly, subjects without MMAS-8 value recorded at a specific visit will be excluded from the analysis of corresponding secondary endpoints.
- Other secondary outcomes in patients with and without advanced educational intervention separately and further outcomes only within pooled patient set (e.g., comorbidities, stroke/thromboembolic/bleeding events, risk factors, ADR, etc.) will all be analyzed in a descriptive manner
- All tests will be done under a statistical level of 0.05.

NIS Protocol Page 33 of 46

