#### 6. RESEARCH METHODS

#### 6.1 STUDY DESIGN

This is a multi-center, 1:1 randomized study to evaluate the effects of educational intervention on adherence to dabigatran, for up to 12 months. The study will be carried out at around 20 hospitals ( $20 \pm 3$ ), where AF patients are mainly treated in Taiwan. A total of 1,200 patients are planned to be enrolled to target 1,000 patients included in the analysis.

Patients newly diagnosed with AF within 1 month, under 75 years old, and newly prescribed with dabigatran on physician's decision per local labelling will be enrolled and equally randomized to receive standard of care (routine clinical practice) or standard of care (routine clinical practice) with advanced educational intervention. To create the randomization numbers, we will use block randomization by Statistical Analysis Software (SAS®) Version 9.4 or higher (SAS Institute, Cary, NC, USA).

The study duration consists of a 1-year enrolment period and a 12-month follow-up period consisting of visits at 3, 6, 9, and 12 months for each individual patient. Being an NIS, the time points of follow-up visits are set in accordance with the routine outpatient follow-ups of AF management in Taiwan. Patients will be continuously followed until death, lost to follow-up, or end of data collection at 12 months, whichever comes first.

The educational materials from "Shared decision making of treatment of NOAC in AF patients" (NTA: 180647) and "Atrial Fibrillation Patient Care in Hospitals" (NTA: 190707) will be used as the educational materials for the experimental group. The education materials will be delivered after randomization (baseline); and at 3, 6, and 9 months thereafter. The adherence to dabigatran will be measured by MMAS-8 score at 3, 6, 9, and 12 months.

The comorbidities, VASc score, and HAS-BLED score will be recorded at baseline; and at 3, 6, 9, and 12 months. Stroke, thromboembolic events, and bleeding-related events will also be captured during 12 months of follow-up.

The whole NIS will be implemented by a Contract Research Organization (CRO) under Local Boehringer Ingelheim's governance.

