## Statistical Analysis Plan (SAP) for Non-Interventional Studies (NIS) BI Study Number 1160-0304

Page 13 of 27

- The educator delivers advanced education to subjects in the experimental group.
- Record the use of dabigatran (dose, date of administration)
- Record the change of concomitant therapies for AF or stroke prevention after baseline (generic name or name of the therapy)
- Complete the measurement of MMAS-8 score
- Record the occurrence of stroke and thromboembolic events, if any
- Record the occurrence of bleeding-related events, if any
- Do safety reporting if any dabigatran relevant ADR, fatal AEs, and pregnancies occurs

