#### 7.1.3 Covariates

Patients recruited will be evaluated for covariates at the visit of baseline. Potential confounders include demographics (age, gender, race, and educational level), VASc score, HASBLED score, comorbidities, concomitant therapies, dose of dabigatran, and renal function.

Statistical methods will be performed to test the difference of covariates between the study group at the visit of baseline (please referred to section 10. data analysis). If any significant difference occurred, linear regression will be conducted to model the relationship between dependent variable and all explanatory variables.

As for linear regression model, the primary endpoint (MMAS-8 score at 12 months) will be considered as dependent variable, and all covariates listed above including study group variable will be considered as explanatory variable.

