#### 10. DATA ANALYSIS

The main and further analysis population will consist of all eligible patients (i.e., all patients who have signed the informed consent and have fulfilled all eligibility criteria).

Continuous variables will be reported as number, mean, standard deviation (SD), minimum, maximum, and 95% confidence interval (CI). Categorical variables will be summarized as number and frequency or percentage with observed (non-missing) data. Missing numbers of both continuous and categorical variables will also be summarized.

As for comparisons of continuous data between baseline and follow-up visit, paired-t test will be performed at the significant level of 0.05. Shapiro—Wilk test will be performed to test the normality of data. When normality assumption is violated, Wilcoxon signed-rank test will be performed instead. On the other hand, McNemar's test will be performed to for comparisons of categorical data between baseline and follow-up visit at the significant level of 0.05.

For the endpoints pre-identified to compare between patients with and without advanced educational intervention, the analyses will be done by independent t-test for continuous data at the significant level of 0.05. Shapiro–Wilk test will be performed to test the normality of data. When normality assumption is violated, Wilcoxon rank-sum test will be performed instead. On the other hand, Chi-square or Fisher's exact test will be performed to for comparisons of categorical data at the significant level of 0.05.

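### No order is stated for the MMAS-8 and the same-visit education session at Months 3, 6 and 9; the questionnaire should come first

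*SAP*

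**What the plan says.** **Education and MMAS-8 at one visit.** Table 1 in both documents marks education at Visits 1 to 4 and the MMAS-8 at Visits 2 to 5, so the two coincide at Visits 2, 3 and 4. The procedure lists for those visits (Protocol 9.2.3.2–9.2.3.4; SAP 6.2.3.2–6.2.3.4) contain the item "The educator delivers advanced education to subjects in the experimental group" and, after two recording items, "Complete the measurement of MMAS-8 score". The rows of Table 1 run in the same order. Visit 5 (Protocol 9.2.3.5; SAP 6.2.3.5) has the MMAS-8 and no education.

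**Use of the scores.** Both documents describe the MMAS-8 as self-report. SAP 10.1 tests it between arms at Months 3, 6, 9 and 12.

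**Baseline wording.** SAP 7.1.2.1, copied from Protocol 9.3.2.4, says: "The validated Chinese MMAS-8 will be used to evaluate the adherence to dabigatran at baseline and every follow-up visit". SAP 6.1 (and Protocol 9.1) says: "The adherence to dabigatran will be measured by MMAS-8 score at 3, 6, 9, and 12 months".

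**Time labels.** Table 1 gives Months 3, 6, 9 and 12 as Weeks 12, 24, 36 and 48, each with a window of 6 weeks either side. The visit headings and the endpoints use months.

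**The concern.** The education session is the randomised intervention, and it is about adherence. The MMAS-8 asks patients to report their own adherence. If the questionnaire follows the session on the same day, patients in the experimental arm answer with the teaching fresh in mind, while control patients answer without it. The score may then reflect what patients have just been told as well as what they did over the preceding months.

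Randomisation does not protect against this, because the difference arises at measurement, after allocation. Analysis cannot repair it either: neither document provides for recording which came first. At stake is whether differences at Months 3, 6 and 9 can be read as differences in adherence.

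The baseline wording and the week labels are separate and smaller matters. They concern whether the text is consistent, not a difference between arms.

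**Working it through.** **1. Which visits are exposed.**

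| Visit | Month | Education | MMAS-8 | Both |
|---|---|---|---|---|
| 1 | 0 | yes | no | no |
| 2 | 3 | yes | yes | yes |
| 3 | 6 | yes | yes | yes |
| 4 | 9 | yes | yes | yes |
| 5 | 12 | no | yes | no |

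The primary endpoint is at Visit 5, so it is not measured on the day of a session.

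**2. How many secondary MMAS-8 comparisons are exposed.** From the list in SAP 10.1:

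| Outcome | Months | Comparisons | At Visits 2–4 |
|---|---|---|---|
| High adherence | 3, 6, 9 | 3 | 3 |
| Medium and low, one table per visit | 3, 6, 9, 12 | 4 | 3 |
| Mean score | 3, 6, 9, 12 | 4 | 3 |
| Total | | 11 | 9 |

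If medium and low are tested separately, the second row becomes 8 and 6. The totals are then 3 + 8 + 4 = 15, of which 3 + 6 + 3 = 12 are exposed. These figures count comparisons; they do not measure bias. Neither document gives a figure from which the size of an order effect could be derived.

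**3. Baseline MMAS-8.**
- For a baseline score: one sentence, appearing in Protocol 9.3.2.4 and SAP 7.1.2.1.
- Against: the design sections list four follow-up times only; the MMAS-8 cell for Visit 1 in Table 1 is empty; the Visit 1 lists have no MMAS-8 item; no stated primary or secondary outcome uses one. The text introducing Table 1 says the table covers all the data to be collected.
- Neutral: patients are "newly diagnosed with non-valvular atrial fibrillation (NVAF) within 1 month and has newly prescribed with dabigatran" before enrolment, so a baseline score would be feasible, but that does not show that one was intended. SAP section 10 plans tests without naming variables ("comparisons of continuous data between baseline and follow-up visit, paired-t test will be performed"). In the regression of SAP 7.1.3, "all covariates listed above including study group variable will be considered as explanatory variable", and that list has no baseline MMAS-8.

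**4. Weeks against months.** The Week row is reproduced exactly by 4 × month: 12, 24, 36, 48. In calendar terms, one month = 365.25 / 12 / 7 = 4.348 weeks.

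| Month | Table 1 week | Calendar week | Offset (weeks) |
|---|---|---|---|
| 3 | 12 | 13.04 | 1.04 |
| 6 | 24 | 26.09 | 2.09 |
| 9 | 36 | 39.13 | 3.13 |
| 12 | 48 | 52.18 | 4.18 |

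For Visit 5 the window is weeks 42–54 on the Week row and 46.18–58.18 on calendar months. The overlap is 54 − 46.18 = 7.82 of 12 weeks, or 65%.

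Whether this matters depends on what the window does. The rule that only in-window values are taken is written for creatinine, eGFR and the HAS-BLED laboratory data. For the MMAS-8, a patient drops out of the primary analysis only if no Month 12 value is recorded, and at the other visits "subjects without MMAS-8 value recorded at a specific visit will be excluded from the analysis of corresponding secondary endpoints". No MMAS-8 is excluded for being out of window. No rule for assigning a score to a visit is stated either.

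**The case against.** The best case for leaving the text alone is that the visit lists are checklists. Nothing calls them sequences, and the Visit 1 list is not a strict chronology: it puts randomisation before the collection of serum creatinine, although creatinine clearance below 30 mL/min is an exclusion. Sites may already give the questionnaire first, in which case the order effect is zero. The protocol calls its analyses mainly descriptive and, in 9.7.1, names only the mean scores for comparison between arms, so the count of 9 of 11 belongs to the SAP. The primary endpoint is untouched.

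All of that stands, and it limits the weight of the point. It does not remove it. No sentence tells sites to give the questionnaire first, every list in both documents shows the other order, and only one arm has the session. Even on the protocol's narrower plan, three of the four mean-score comparisons fall at the exposed visits.

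On the baseline wording, a reader might infer that the intent cannot be determined. The documents do not support that. Table 1, the design sections and the Visit 1 lists agree, and the one sentence copied between the documents is the outlier. Nor can the unnamed variables in the SAP section 10 paired tests be held against the plan: parts of the SAP are not available in the public text and may name them.

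**Conclusion.** The point holds as a missing instruction on conduct. At Months 3, 6 and 9 the plan allows the self-report outcome to be taken straight after the intervention in one arm only, and the order of its own lists invites this. It reaches 9 of the 11 secondary MMAS-8 comparisons in SAP 10.1, or 12 of 15 on the finer count. That bias occurs rests on the assumption that at least some sites follow the list order. Its size is unknown. The change is worth making because it removes the possibility at almost no cost.

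Two stronger conclusions might be drawn, and neither is supported:
- **That the primary result is biased.** Visit 5 has no education session, so the 12-month comparison is not exposed to this mechanism. A randomised comparison at 12 months does not need a baseline MMAS-8 either.
- **That the Week 48 label alters the primary endpoint.** It is a four-weeks-per-month convention, the same in both arms, and no stated rule discards or reassigns an MMAS-8 by its date.

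The baseline sentence and the Week row are therefore wording points only.

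**What to change.** 1. Add one line to Protocol 9.2.3.2–9.2.3.4 and SAP 6.2.3.2–6.2.3.4: the MMAS-8 is completed before that visit's education session. Tell sites by memo. If some of these visits have already taken place, they cannot be re-ordered; give the start date of the rule in the study report.
2. Minor: reconcile the baseline wording in Protocol 9.3.2.4 and SAP 7.1.2.1 with Table 1, the design sections and the Visit 1 lists. If the sponsor did intend a baseline score, the same order line is needed at Visit 1, which also has an education session, and the SAP should say whether the section 10 paired tests include it.
3. Minor: reconcile the Week and Month rows of Table 1 in both documents.

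The cost is six short insertions (three visits in two documents), two wording corrections and a memo. No visit or procedure is added, unless a baseline questionnaire is confirmed as intended. Only the first item is time-critical.

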#### 7.1.2.2 Secondary outcomes

- (1) The proportion of patients with high adherence to dabigatran treatment which is defined as achieving the MMAS-8 score of 8 points at 3, 6, and 9 months in patients with and without advanced educational intervention
- (2) The proportion of patients with medium (MMAS-8 score: 6-7 points) and low (MMAS-8 score < 6 points) adherence to dabigatran treatment at 3, 6, 9, and 12 months in patients with and without advanced educational intervention
- (3) The mean MMAS-8 score at 3, 6, 9, and 12 months in patients with and without advanced educational intervention
- (4) The discontinuation rate of dabigatran and reasons for discontinuation (switch or stop treating dabigatran) in patients with and without advanced educational intervention

